7.6 Protocol-Defined Events of Special Interest

The following are events of special interest and will need to be reported expeditiously.

7.6.1 Pregnancy, abortion, birth defects/congenital anomalies

Female patients who are not of child-bearing potential (see *Appendix A*) and female patients of child-bearing potential who have a negative serum pregnancy test (within 72 hours prior to initiation of study drug) are eligible for the study. Female patients of child-bearing potential (see *Appendix A*), must consent to use a medically acceptable method of contraception throughout the study period and for 4 weeks after the last dose of Tenalisib. A barrier method of contraception must be included.

During the course of the trial, all female patients of childbearing potential (the definition of "women of *childbearing* potential" is listed in *Appendix A*) must contact the treating investigator immediately if they suspect that they may be pregnant (a missed or late menstrual period should be reported to the treating investigator).

If an investigator suspects that a patient may be pregnant prior to administration of trial drug(s), the trial drug(s) must be withheld until the result of the pregnancy test is confirmed. If a pregnancy is confirmed, the patient must not receive any trial drug(s) and must be discontinued from the trial.

If an investigator suspects that a patient may be pregnant after the patient has been receiving trial drug(s), the trial drug(s) must immediately be withheld until the result of the pregnancy test is confirmed. If a pregnancy is confirmed, the trial drug(s) must be immediately and permanently stopped, the patient must be discontinued from the trial, and the investigator must notify the Medical Monitor as soon as possible. A pregnancy Form should be completed and emailed to Sponsor.

Congenital anomalies/birth defects always meet SAE criteria, and should therefore be expeditiously reported as an SAE, using the previously described process for SAE reporting. A Pregnancy Form should also update to reflect the outcome of the pregnancy.

7.6.2 Overdose

Both intentional (misuse/abuse) and unintentional (accidental) overdose must be reported in the CRF. Symptomatic unintentional and intentional overdose must be reported as AE in the CRF (see below). Any accidental overdose with the study drug that is symptomatic, fulfilling a seriousness criterion, is to be reported to the Sponsor immediately (within 24 hrs) as SAE. Intentional overdose should be reported as an SAE irrespective of seriousness criteria.

CONFIDENTIAL Page 43 of 61

Version: 1.0, Dated 12 September 2019

Type of overdose	Document in AE in CRF CRF		Complete SAE form	
Unintentional (accidental)	Yes	Only if associated with an AE	Only if associated with an SAE	
Misuse/Abuse	Yes	Yes	Yes, even if not associated with a SAE	

7.7 **Dose Modifications**

In case of the hematologic and non-hematologic toxicities, the dose modifications provided below (Table 4 and Table 5) should be used a guidance and should be determined as per PI's clinical judgement. The dose modifications are intended to be applied when the investigator determines the events related to Tenalisib. If events (cytopenia) are deemed related to the underlying disease rather than Tenalisib, dose reduction will be done as per the investigator's discretion.

In case of drug withhold, Tenalisib treatment can be resumed if:

- Patient recovered from grade 3-4 toxicity as defined in dose modification guidance below.
- No clinical or radiographic evidence of disease progression.
- Investigator believes the risk of progression outweighs the risk of further treatment.

If treatment is delayed >2 weeks, treatment continuation should be discussed with Medical monitor. The treatment should be permanently discontinued if withhold of study drug due to drug related toxicity is for > 28-days unless approved by medical monitor.

At the discretion of the investigator, a dose re-escalation may be permitted for patients who earlier has dose reduction. The decision should be taken after evaluating the emerging safety data and benefit and risk of re-escalation. Drug holidays are discouraged. Any patient in whom similar toxicity recurs at the reduced dose, it should be discussed with medical monitor to determine appropriate strategy on treatment continuation.

Table 4: Dose Modifications for Hematologic Toxicity

CTCAE Grade Toxicity	Action to be Taken			
Hematologic				
Neutropenia (ANC)				
Grade 3 $1.0 \times 10^9/L < ANC \ge 0.5 \times 10^9/L$	Maintain Tenalisib dose. Monitor ANC at least weekly.			
Grade 4 0.5 x 10 ⁹ /L <anc< td="">First incidence: Withhold* dose until resolved to ≤ Grade 2 or baseline. Monitor ANC at least weekly. Resume treatment at the same dose level. Subsequent occurrence: Hold dose until resolved to ≤ Grade 2 or baseline. Consider growth factor support. Resume treatment at the reduced dose level (Tenalisib 400 mg BID) if warranted.	</anc<>	First incidence: Withhold* dose until resolved to ≤ Grade 2 or baseline. Monitor ANC at least weekly. Resume treatment at the same dose level. Subsequent occurrence: Hold dose until resolved to ≤ Grade 2 or baseline. Consider growth factor support. Resume treatment at the reduced dose level (Tenalisib 400 mg BID) if warranted.			
Grade 3 Febrile neutropenia ANC <1.0 X 10 ⁹ /L with a single temperature of > 38.3 °C (101 °F)	Withhold* dose until resolved to ≤ Grade 2 or baseline, consider growth factor support, then reduce by 1 dose level (Tenalisib 400 mg BID), if warranted. If the			

CONFIDENTIAL Page 44 of 61

or a sustained temperature of \geq 38 °C (100.4 °F) for more than one hour.	ANC is <1 X 10^9 /L $(1000/\mu L)$ before therapy, the dose shall not be modified as long as ANC >0.5 X 10^9 /L.		
Thrombocytopenia			
Grade 3 thrombocytopenia [#] with Grade 1 bleeding	Maintain Tenalisib dose. Monitor platelet count at least weekly.		
Grade 3 thrombocytopenia [#] with Grade 2 bleeding	1st occurrence : Withhold** dose until to ≤ Grade 2 or baseline or resolution of bleeding. Consider platelet transfusion as necessary. Resume treatment at the same dose level.		
OR Grade 4 thrombocytopenia [#] (20.0 X 10 ⁹ /L< PLT)	Subsequent Occurrences: Withhold dose until to ≤ Grade 2 or baseline or resolution of bleeding. Consider platelet transfusion as necessary. Resume treatment at the reduced dose level (Tenalisib 400 mg BID) if warranted. Doses should not be modified if Grade 4 thrombocytopenia is present at baseline.		

^{*} The treatment should be permanently discontinued if withhold of study drug due to drug related toxicity is for > 28days unless approved by medical monitor.

** Patient receiving concomitant medication (e.g. anti-platelets, aspirin, or low molecular weight heparin) should be

Table 5: Dose Modifications for Non-Hematologic Toxicities

Non- Hematologic	Action to be Taken Grade 3 or higher sepsis or pneumonia Withhold Tenalisib until infection has resolved. Restart at the same or at the reduced dose (Tenalisib 400 mg BID)			
Infection				
Skin rash	Grade 1-2			
(Cutaneous reactions)	 Maintain Tenalisib dose. Initiate supportive care with emollients, antihistamines (for pruritus), or topical steroids Monitor closely until resolved. 			
	Grade 3			
	 Withhold Tenalisib dose. Initiate supportive care with emollients, antihistamines (for pruritus), or topical steroids Monitor at least weekly until resolved. 			
	Restart Tenalisib at the reduced dose level (Tenalisib 400 mg BID).			
	If severe cutaneous reaction does not improve, worsens, or recurs, discontinue Tenalisib			
	Life threatening or SJS, TEN, DRESS (any grade)			
	Discontinue Tenalisib permanently.			
Pneumonitis	Moderate (Grade 2) symptomatic pneumonitis			
without suspected	• Withhold Tenalisib dose. Initiate systemic steroid therapy. If pneumonitis recovers to Grade 0 or 1, Tenalisib may be resumed at reduced dose.			
infectious cause	• If non-infectious pneumonitis recurs or patient does not respond to steroid therapy, discontinue Tenalisib.			

CONFIDENTIAL Page 45 of 61

discussed with the medical monitor for further management.

[#] Refer iwCLL criteria

	Severe (Grade 3) or life-threatening pneumonitis
	Discontinue Tenalisib. Treat with systemic steroid therapy.
NI C	Moderate diarrhea and responsive to antidiarrheal agents:
Non-infectious Diarrhea	Maintain Tenalisib dose. Monitor at least weekly until resolved.
	Moderate diarrhea and unresponsive to antidiarrheal agents:
	• Withhold Tenalisib dose. Initiate supportive therapy with enteric acting steroids (e.g., budesonide).
	Monitor at least weekly until resolved.
	• Restart Tenalisib at the reduced dose level (Tenalisib 400 mg BID).
	Severe diarrhea or hospitalization
	• Withhold Tenalisib dose. Initiate supportive therapy with enteric acting steroids (e.g.,
	budesonide) or systemic steroids.
	Monitor at least weekly until resolved.
	• Restart Tenalisib at the reduced dose level (Tenalisib 400 mg BID).
	Life threatening diarrhoea • Discontinue Tenalisib permanently.
Hepatic*	Transaminitis
Перапе	Grade 1-2 Transaminitis (ALT/AST >1-3 x ULN if baseline is normal; 1.5 - 3 x baseline
	if baseline is abnormal):
	Maintain Tenalisib dose and initiate prednisone 40 mg daily.
	Monitor AST/ALT weekly until resolved and then taper steroid.
	• Withhold Tenalisib in case of development of grade 2 transaminitis or worsening of
	Grade 1 transaminitis while on steroids.
	Grade 3 Transaminitis (ALT/AST >5-20 x ULN; >5-20 x baseline if baseline is
	abnormal):
	• Withhold Tenalisib and monitor ALT/AST twice a weekly until Grade ≤1; restart Tenalisib at one dose lower (Tenalisib 400 mg BID).
	• Initiate prednisone 1 mg/kg in case no improvement after withholding Tenalisib for 1 week.
	 Monitor ALT/AST twice a weekly until Grade ≤1; restart Tenalisib at one dose lower (Tenalisib 400 mg BID). and taper steroid.
	• If no immediate response to steroids within 7 days, initiate mycophenolate mofetil.
	 In case of recurrence of transaminitis at reduced doses, discontinue Tenalisib permanently after assessing risk versus benefit.
	Grade 4 Transaminitis (ALT/AST >20 x ULN; >20 x baseline if baseline is abnormal):
	 Tenalisib should be permanently discontinued. Bilirubin:
	• Grade 2 (> 1.5-3 x ULN; >1.5- 3 x baseline if baseline is abnormal): Maintain
	 Tenalisib dose. Monitor at least weekly until ≤ 1x ULN Grade 3 (> 3-10 x ULN; >3 - 10 x baseline if baseline is abnormal): Withhold Tenalisib. Monitor at least weekly until bilirubin is≤ 1x ULN; Restart Tenalisib at one dose lower (Tenalisib 400 mg BID).
	Grade 4 (> 10 x ULN; >10 x baseline if baseline is abnormal): Discontinue Tenalisib permanently
Other Non- Hematologic	Action to be Taken
Grade 1 or 2	None
HAUC I OF Z	None

CONFIDENTIAL Page 46 of 61

Rhizen Pharmaceuticals S.A.

Protocol No. RP6530-1901 Version: 1.0, Dated 12 September 2019

Grade 3 Withhold Tenalisib dose until toxicity Grade ≤2. Restart Tenalisib at one dose lower (Tenalisib 400 mg BID) if warranted.				
Recurrence of grade 3 toxicity	Withhold Tenalisib dose until toxicity Grade ≤2; Restart Tenalisib at one dose lower or discontinue treatment			
Grade 4	Withhold Tenalisib dose until toxicity Grade ≤2; Restart Tenalisib at one dose lower (Tenalisib 400 mg BID) or discontinue Tenalisib			
Recurrence of grade 4 toxicity	Discontinue Tenalisib			

^{*} The treatment should be permanently discontinued if withhold of study drug due to drug related toxicity is for > 28-days unless approved by medical monitor.

CONFIDENTIAL Page 47 of 61

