4 SELECTION AND WITHDRAWAL OF SUBJECTS

4.1 Inclusion Criteria

Patients must meet all the following inclusion criteria to be eligible for participation in this study:

- 1. Patients with diagnosis of B-cell CLL as confirmed by histopathology or flow cytometry.
- 2. Disease status defined as refractory to or relapsed after at least one prior therapy.
- 3. Presence of measurable lymphadenopathy, defined as the presence of ≥ 1 nodal lesion that measures ≥ 1.5 cm in the longest diameter (LD) as assessed by computed tomography (CT).
- 4. ECOG performance status ≤ 2 .
- 5. Male or female ≥ 18 years of age.
- 6. Life expectancy of at least 3 months.
- 7. Adequate bone marrow (BM), liver, and renal function as assessed by the following laboratory requirements conducted within 14 calendar days before starting study treatment.
 - a. Adequate bone marrow function:
 - I. Haemoglobin ≥ 9 g/dl
 - II. Absolute neutrophil count (ANC) $\geq 1 \times 10^{9}/L$
 - III. Platelets $>50 \times 10^{9}/L$

Patients with hemoglobin, neutrophil and platelet counts below the above specified values will be eligible if it is due to tumor dissemination or infiltration to bone marrow and as per physician's discretion. Hemoglobin and platelet requirements should not be met by use of recent transfusion or growth factor support (G-CSF or erythropoietin) within 3 weeks prior to assessment.

- b. Adequate liver function:
 - I. Total bilirubin ≤ 1.5 times the upper limit of normal (ULN)
 - II. ALT and AST should be ≤ 3 x ULN. ALT and AST ≤ 5 x ULN if known liver involvement.
- c. Adequate renal function: Calculated creatinine clearance ≥ 50 mL/min (as calculated by the Cockcroft-Gault method) or Creatinine ≤ 1.5 mg/dl.
- 8. Ability to swallow and retain oral medication.
- 9. Female patients who are not of child-bearing potential, and female patients of child-bearing potential should have a negative serum pregnancy test within 3 days prior to Cycle 1 Day 1 (C1D1). Female patients of child-bearing potential must consent to use a medically acceptable method of contraception as defined in *Appendix A*, throughout the study period and for 30 days after the last dose of study drug.

Protocol No: RP6530-1901 Version: 1.0, Dated 12 September 2019

- 10. Male patients willing to use adequate contraceptive measures throughout the study period and for 12 weeks after the last dose of Tenalisib.

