7.4 Severity of Adverse events

Severity of adverse events will be assessed according to National Cancer Institute (NCI)- CTCAE v5.0 with exceptions for platelet, hemoglobin and ANC that are recommended by iwCLL guidelines for the CLL (see below).

Grade*	Decrease in platelet† or Hb‡ (nadir) from baseline, %	Absolute neutrophil count (nadir)§ x 10 ⁹ /L	
0	No change to 10	≥2	
1	11-24	\geq 1.5 and \leq 2	
2	25-49	$\geq 1 \text{ and } < 1.5$	

CONFIDENTIAL Page 40 of 61

Version: 1.0, Dated 12 September 2019

3	50-74	≥0.5 and <1	
4	≥ 75	< 0.5	

^{*} Grades: 1-mild; 2-moderate; 3-severe; 4-life-threatening; 5-fatal. Death occurring as a result of toxicity at any level of decrease from baseline will be recorded as grade 5.

§ If the absolute neutrophil count (ANC) reaches $<1\times10^9/L$, it should be judged to be grade 3 toxicity. Other decreases in the white blood cell count or in circulating granulocytes are not to be considered because a decrease in the white blood cell count is a desired therapeutic end point. A gradual decrease in granulocytes is not a reliable index in CLL for stepwise grading of toxicity. If the ANC is $<1\times10^9/L$ before therapy, the patient is not evaluable for toxicity referable to the ANC. The use of G-CSF is irrelevant for the grading of toxicity but should be documented.

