7.5.2 Persistent or recurrent adverse events

A persistent AE is one that extends continuously, without resolution, between patient evaluation time points. Such events should only be recorded once on the SAE Report Form. If a persistent AE becomes more severe or lessens in severity, AE should be recorded separately with onset date as date of change of severity in CRF.

A recurrent AE is one that occurs and resolves between patient evaluation time points, and subsequently recurs. All recurrent events should be recorded separately on an SAE Report Form and/or CRF.

CONFIDENTIAL Page 41 of 61

[†] Platelet counts must be below normal levels for grades 1-4. If, at any level of decrease the platelet count is $<20 \times 10^9/L$, this will be considered grade 4 toxicity unless a severe or life-threatening decrease in the initial platelet count (e.g., $20 \times 10^9/L$) is present at baseline, in which case the patient is not evaluable for toxicity referable to platelet counts.

[‡] Hb levels must be below normal levels for grades 1-4. Baseline and subsequent Hb determinations must be performed as per the schedule of events. The use of erythropoietin is irrelevant for the grading of toxicity but should be documented.

Version: 1.0, Dated 12 September 2019

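### Table 4's shared release clause for thrombocytopenia, read literally, lets a Grade 4 patient who bled restart when bleeding stops, with the count still Grade 4

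*Protocol*

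**What the plan says.** Protocol section 7.7, Table 4, handles thrombocytopenia in two rows.

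- Grade 3 with Grade 1 bleeding: the patient stays on drug ("Maintain Tenalisib dose. Monitor platelet count at least weekly").
- Grade 3 with Grade 2 bleeding, OR Grade 4: one shared action. At the first occurrence the drug is withheld ("dose until to ≤ Grade 2 or baseline or resolution of bleeding") and then resumed at the same dose. At later occurrences the same clause applies, with restart at 400 mg BID if warranted. The row's only exception is "Doses should not be modified if Grade 4 thrombocytopenia is present at baseline".

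The Grade 4 trigger is printed as "20.0 X 10 ⁹ /L< PLT", and a footnote to the thrombocytopenia grades says "Refer iwCLL criteria".

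The grading itself is in section 7.4. Its platelet column is headed "Decrease in platelet† or Hb‡ (nadir) from baseline", with Grade 2 at a fall of 25-49%, Grade 3 at 50-74% and Grade 4 at 75% or more. A footnote adds that for any count below 20 × 10⁹/L "this will be considered grade 4 toxicity unless a severe or life-threatening decrease in the initial platelet count" is present at baseline; its example of such a baseline is 20 × 10⁹/L.

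Section 4.1 sets the usual platelet entry limit at 50 × 10⁹/L, but patients below it "will be eligible if it is due to tumor dissemination or infiltration to bone marrow", at the physician's discretion.

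**The concern.** The release conditions are joined by *or*, and nothing links the bleeding condition to the Grade 3 trigger. Taken as written, resolution of bleeding alone ends the hold for a Grade 4 patient who bled, whatever the count.

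That result does not fit the rest of the table. Grade 4 without any bleeding is itself a reason to hold in the same row, so the released patient meets the trigger again at once. Grade 4 neutropenia, a few rows above, is released only on count recovery (Grade 2 or better, or baseline).

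The bleeding condition does make sense for the Grade 3 trigger, because a Grade 3 patient with only Grade 1 bleeding is kept on drug. The problem is that one clause serves both triggers.

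What is at stake is dosing safety for a Grade 4 patient who bled. Adverse event grading follows section 7.4, not Table 4. ORR, DoR, alpha and power are untouched.

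**Working it through.** **Step 1: the rule applied to three patients** (bleeding, where present, has stopped; count still Grade 4).

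| Patient | Starts a hold? | Literal clause allows restart? |
|---|---|---|
| Grade 3, bled at Grade 2 | Yes | Yes, consistent with the row above |
| Grade 4, never bled | Yes | Unclear: there is no bleeding to resolve |
| Grade 4, bled | Yes | Yes, through resolution of bleeding |

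The table layout may have been disturbed in extraction. If the first-occurrence cell belonged only to Grade 3 and the later-occurrence cell only to Grade 4, both cells would still carry the same clause.

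**Step 2: does another rule close the gap?** Section 7.7 requires recovery from Grade 3-4 toxicity before restart, but defines recovery by the table itself, so it leads back to this clause. It also requires no progression and an investigator risk judgement. Neither sets a platelet count.

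**Step 3: how far short of recovery the count can be.** Let B be the baseline platelet count (all counts × 10⁹/L). From section 7.4:

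- Grade 4 ceiling = max(20, 0.25B), from the below-20 rule and the 75% fall.
- Count recovery to Grade 2 or better = max(20, 0.50B), because Grade 3 starts at a 50% fall and any count below 20 is Grade 4.
- For B of 20 or more, max(20, 0.50B) does not exceed B, so a return to baseline is never the easier condition.
- Minimum shortfall = recovery − ceiling: 0 for B ≤ 40; 0.50B − 20 for 40 < B ≤ 80; 0.25B for B > 80.

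| B | Ceiling | Recovery | Minimum shortfall |
|---|---|---|---|
| 30 | max(20, 7.5) = 20 | max(20, 15) = 20 | 0 |
| 40 | max(20, 10) = 20 | max(20, 20) = 20 | 0 |
| 50 | max(20, 12.5) = 20 | max(20, 25) = 25 | 5 |
| 80 | max(20, 20) = 20 | max(20, 40) = 40 | 20 |
| 100 | max(20, 25) = 25 | max(20, 50) = 50 | 25 |

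The value 50 is the usual entry limit, 40 and 80 are the break points of the formula, and 30 and 100 are assumed baselines.

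**Step 4: the shortfall is a minimum.** It is measured from the top of the Grade 4 range, and a real count can be lower.

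- B = 30, count 15: below 20, so Grade 4. Recovery needs 20, so the count is 20 − 15 = 5 short, yet the literal clause releases the patient.
- B = 100, count 15: Grade 4. Recovery needs about 50, so the count is 50 − 15 = 35 short, and the literal clause again releases.

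The clause therefore matters at any baseline where the count is still Grade 4 and below baseline, including baselines of 20 to 40.

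**Step 5: the printed signs.** Section 7.4 makes counts below 20 Grade 4; Table 4 appears to print the reverse. The Grade 3 and Grade 4 neutrophil cells appear reversed against section 7.4 too, while the febrile neutropenia cell prints its neutrophil limit in the usual direction.

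**The case against.** The best defence is that each release condition belongs to its own trigger: count recovery for the count trigger, bleeding resolution for the bleeding trigger. Resolution of bleeding means nothing for a Grade 4 patient who never bled. Grade 4 alone is a hold trigger, so the row could be said to correct itself, and a patient still at Grade 4 is hard to call recovered. This is probably what was meant. It is not what the row says, and the general recovery condition defers to the row.

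The safeguards are real. The tables are guidance under the investigator's judgement and apply to events judged related to Tenalisib. Delays over 2 weeks, recurrence at the reduced dose, and patients on antiplatelet drugs or LMWH go to the medical monitor, who also reviews adverse events regularly (section 12.3). None of these requires a Grade 4 count to recover, and a restart within 2 weeks does not prompt the time-based discussion.

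The scenario may also be uncommon. Thrombocytopenia is not among the reported toxicities singled out in section 3.5.5 (ALT/AST increase, rash, neutropenia), nor among the DLTs in the clinical summary (transaminitis, rash).

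A reader might infer that the reversed signs are an established protocol error that would send drug to patients below 20. The documents do not support that. The extracted text is visibly corrupted at the Grade 4 neutrophil sign, and the table's footnote together with section 7.4 makes the intended direction clear. The repeated pattern suggests a source error but does not prove one.

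**Conclusion.** The concern holds as a minor drafting defect: a stated dosing rule, read literally, permits restart at a Grade 4 platelet count after bleeding stops. The minimum shortfall from count recovery is 0 at baselines of 40 × 10⁹/L or less, 5 at 50, 20 at 80 and 25 at 100. These are differences between thresholds, not measures of patient impact.

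Two inferences should be resisted. The zero at low baselines does not mean that the clause is harmless there, as baseline 30 with count 15 shows. Nor do the documents show that any patient restarted at Grade 4 or came to harm: they give no frequency of Grade 4 thrombocytopenia and no dosing records.

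The conclusion assumes that the extracted clause matches the source. The low-baseline example also assumes that a baseline of 30 remains evaluable under the section 7.4 footnote.

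Severity stays minor because the table is guidance, no endpoint changes, and SAP sections 5.1 and 6 record closure after Stage 1 with 21 patients enrolled.

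**What to change.** Split the release by trigger, for first and subsequent occurrences:

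- **Grade 4:** hold until the count is back to Grade 2 or better, or to baseline, *and* any bleeding has resolved.
- **Grade 3 with Grade 2 bleeding:** keep the present clause.
- Keep the sentence on Grade 4 already present at baseline.

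Check the platelet and neutrophil signs against the source PDF. If the reversal is confirmed, align them with section 7.4: platelets <20 × 10⁹/L or a fall of at least 75% for Grade 4; ANC <0.5 for Grade 4, and ≥0.5 to <1.0 for Grade 3 (× 10⁹/L).

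This is wording only, with no new data or visits. There are two costs. Some Grade 4 patients who bled would be held longer, and more would reach the 2-week discussion and the 28-day discontinuation rule. Where a site has applied only the printed 20 cut-off, patients who are Grade 4 by percentage fall would now be held: at baseline 200 and count 45 the fall is 155/200 = 77.5%. Grade 3 release is unchanged.

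The split does not settle whether a transfused count qualifies as recovery. The row allows transfusion, and the present clause leaves the same question open.

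Since the study has closed, the change serves later protocols that reuse the table. For this study, the report could optionally list platelet counts at hold and at resumption for any thrombocytopenia interruption, using the laboratory and exposure listings already planned (SAP sections 10.6.3 and 12).

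### Table 5 can be read as either maintaining or withholding Tenalisib for a patient first seen with Grade 2 transaminitis, and gives no recovery grade or restart dose for that hold

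*Protocol*

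**What the plan says.** Four places in the protocol bear on this.

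- **Section 7.7, Table 5, Hepatic, Grade 1-2 row.** The row is headed "Grade 1-2 Transaminitis (ALT/AST >1-3 x ULN if baseline is normal; 1.5 - 3 x baseline", and the line continues for an abnormal baseline. Its first bullet is "Maintain Tenalisib dose and initiate prednisone 40 mg daily". The second asks for weekly AST/ALT until resolution and then a steroid taper. The third begins "Withhold Tenalisib in case of development of grade 2 transaminitis or worsening of" and finishes "Grade 1 transaminitis while on steroids".
- **Section 7.7, text before the tables.** The first condition for resuming after a hold is "Patient recovered from grade 3-4 toxicity as defined in dose modification guidance below". A delay of more than 2 weeks is to be discussed with the medical monitor.
- **Section 7.7, limit on holds.** "The treatment should be permanently discontinued if withhold of study drug due to drug related toxicity is for > 28-days unless approved by medical monitor". The footnote to the hepatic block repeats this.
- **Section 3.5.5.** A bullet naming raised ALT/AST, rash and neutropenia says to interrupt Tenalisib at Grade 3 or higher.

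Section 7.7 also says that the tables are guidance, subject to the investigator's judgement, for events considered related to Tenalisib.

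**The concern.** One row covers Grades 1 and 2 together. It starts with an instruction to continue and ends with an instruction to hold that names Grade 2. Two sites following the text in good faith can act differently on the same first-presentation Grade 2 patient. Once a patient is held under this row, nothing in it says when or at what dose treatment resumes.

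The organ matters. Section 1.2 reports the liver as a target organ in the toxicity studies, and Section 1.3 lists Grade 3 transaminitis among the dose-limiting toxicities of the earlier T-cell lymphoma study.

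The data are touched too. The SAP counts patients with dose reductions or interruptions (10.1), summarises exposure and compliance (10.6.1), and tabulates adverse events that led to interruption or reduction (10.6.2). Part of what those tables show could reflect how a site parsed one sentence.

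**Working it through.** The plan states no figure on this point, so there is none to reproduce. The check is a reading of the row under each grammatical possibility.

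**Step 1. Two readings of the third bullet.**

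- *Narrow:* the steroid condition attaches only to worsening of Grade 1. Any development of Grade 2 triggers a hold.
- *Wide:* the condition attaches to both triggers. Grade 2 triggers a hold only if it develops on steroids.

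| Patient | Narrow reading | Wide reading |
|---|---|---|
| Grade 1, steroid not yet started | Maintain | Maintain |
| Grade 1 on prednisone, worsens | Withhold | Withhold |
| Grade 1 on prednisone, reaches Grade 2 | Withhold | Withhold |
| First seen at Grade 2, not on steroids | Withhold by bullet 3, maintain by the heading and bullet 1 | Maintain and start prednisone |
| First seen at Grade 2, then on prednisone without improvement | Already held by bullet 3 | No clear trigger: Grade 2 did not develop on steroids, and the worsening limb names only Grade 1 |

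The readings agree on the first three lines and part on the last two. The ambiguity is therefore confined to patients who enter the row at Grade 2.

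**Step 2. Section 3.5.5.** Its threshold for interruption is Grade 3 or higher. Table 5 holds at Grade 2 in at least one situation under either reading. Section 3.5.5 does not forbid an earlier interruption, but it does not help a site choose between the readings.

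**Step 3. Terms for ending the hold.** Every other hold in Tables 4 and 5 states a recovery condition and a dose on restart, or an explicit choice of dose or discontinuation: neutropenia, febrile neutropenia, thrombocytopenia, infection, rash, pneumonitis, diarrhoea, Grade 3 transaminitis, Grade 3 bilirubin and other Grade 3 or 4 events. The hold in the Grade 1-2 transaminitis row states neither. The resumption list in Section 7.7 does not fill the gap, because its recovery condition refers to Grade 3-4 toxicity.

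**Step 4. What bounds the hold.** Two general provisions still apply: discussion after more than 2 weeks, and discontinuation after more than 28 days unless approved. Planned treatment is 7 cycles x 28 days = 196 days. A hold that runs to the limit without approval takes 28 / 196 = 1/7, about 14% of planned treatment. This is a ceiling on one unapproved hold, not an expected loss.

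**Step 5. Where it would appear in the data.** SAP 10.6.1 defines exposure as last dosing day minus first dosing day plus 1. A hold followed by resumption does not shorten that figure. It appears in the interruption counts. Exposure falls only if the patient does not restart.

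**Step 6. Grade limits printed in the row.** For a normal baseline, the Grade 1-2 row covers more than 1 and up to 3 x ULN, and the Grade 3 row starts above 5 x ULN. No cut-off between Grades 1 and 2 is printed, and values above 3 and up to 5 x ULN fall in no row. The same gap exists for multiples of an abnormal baseline. The table therefore does not itself mark the Grade 2 value that triggers the hold. The conclusion does not depend on this, but it adds to the uncertainty.

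**The case against.** The strongest reply is that the row is a sequence: continue and start prednisone, monitor weekly, and hold if the patient reaches Grade 2 or worsens from Grade 1 despite the steroid. The word development suggests a change during follow-up. Treating a patient who worsens on steroids differently from one who has not yet had them is not inconsistent. This stands. A reader might infer that the row flatly contradicts itself for every Grade 2 event. The text does not establish that, because on the sequential reading the bullets agree for patients who escalate on steroids. The wording does not compel that reading, however, and even if it is adopted, the patient who enters at Grade 2 and fails to improve has no clear instruction.

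A reader might also infer that a held patient has no way back onto drug. That goes too far. Nothing bars resumption, the tables are guidance, and the medical monitor is brought in after 2 weeks and can approve a hold beyond 28 days. What remains is an omission: no recovery grade and no restart dose.

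Finally, the SAP (Sections 5.1 and 6) records that 21 patients were enrolled in Stage 1 and that Stage 2 will not be initiated. The practical gain from rewording is therefore limited to interpreting the data and to any later use of the table. That also stands.

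**Conclusion.** The point holds as an ambiguity and an omission. The Grade 1-2 transaminitis row supports two different actions for a patient first seen at Grade 2, Section 3.5.5 gives a third place to look without settling the matter, and the hold lacks a recovery grade and a restart dose.

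Its size cannot be computed. The documents give no Grade 2 transaminitis rate and no split by steroid use at onset. One could say that all such first-presentation patients are held under one reading and none under the other, but that only restates the two readings and is not an expected frequency. The one figure available is the ceiling of 28 of 196 planned days for a single hold without approval.

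The consequence lies in patient safety and in the interruption and exposure summaries. It does not alter the Simon design figures: the 40% and 60% response rates, the stage sizes of 20 and 41, and the boundaries of 8 and 31 do not depend on it. The conclusion assumes that the row was extracted from the protocol with its bullets in the printed order.

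**What to change.** The sponsor's medical expert should reconcile Section 3.5.5, the resumption list in Section 7.7 and the Grade 1-2 transaminitis row of Table 5, so that:

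- Grade 1 and Grade 2 each carry one unambiguous instruction, stated with and without ongoing steroids;
- the resumption conditions cover any Grade 2 hold that the table keeps;
- Section 3.5.5 agrees with whatever the table then says.

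Which action, grade or dose applies is a clinical decision, and none is proposed here.

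The cost is wording in one table block and its two related passages. For the patients already treated, the study report could note, from the adverse event and dosing data already collected, what was done at each Grade 2 transaminase event, so that the interruption counts can be read with the ambiguity in mind. This needs no change to the design or to the efficacy analysis.
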